Amendment 08	22-Mar-2017	In order to further explore an emerging efficacy signal, additional patients with previously untreated metastatic melanoma (ie, no prior systemic anticancer therapy for unresectable or metastatic melanoma) subjects with PD-L1 negative tumors (<1%) will be enrolled under this amendment.
Revised Protocol 05	09-May-2016	Incorporates Amendment 06 and Administrative Letters 04 and 05
Amendment 06	09-May-2016	To include a cohort of NSCLC and melanoma subjects who have relapsed or are refractory to prior anti-PD-1/anti-PD-L1 therapy.
Administrative Letter 05	01-Jun-2016	To clarify application to new cohort of subjects with NSCLC and melanoma who have relapsed or are refractory to prior anti-PD-1/anti-PD-L1) therapy and exception for NSCLC and MEL subjects enrolling in the expansion cohorts where prior anti-PD-1 or anti-PD-L1 therapies are specifically required.
Administrative Letter 04	19-Jan-2016	Change in MM
Revised Protocol 04	22-Dec-2015	Incorporates Amendment 05
Amendment 05	22-Dec-2015	To expand the study population for cohort expansion to include subjects with follicular lymphoma and to further differentiate subjects with non-small-cell lung cancer into two separate groups (those with no prior anti PD-1/anti-PD-L1 therapy and those who have relapsed or are refractory to prior anti-PD-1/anti-PD-L1).
Revised Protocol 03	30-Aug-2015	Incorporates Amendment 04 and Administrative Letter 03
Amendment 04	30-Aug-2015	Discontinue enrollment into Cohorts A, B, C, D. Implement an update to exclusion Criteria
Admin Letter 03	26-Aug-2015	Discontinue enrollment into Cohorts A, B, C, D during cohort expansion
Revised Protocol 02	29-Jun-2015	Incorporates Amendment 03
Amendment 03	29-Jun-2015	To implement a change in duration to combination therapy and use of flat dosing for subjects enrolled following approval of Revised Protocol 02
Revised Protocol 01	06-Mar-2015	Incorporate Amendment 02
Amendment 02	06-Mar-2015	To implement changes to inclusion/exclusion criteria, clarify requirements and assessments for treatment beyond disease progression and criteria for allowing treatment to resume after a dose delay due to toxicity, add time and events schedules for subjects eligible for retreatment, and clarify PK sampling and biomarker assessments.

Document	Date of Issue	Summary of Change

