3.1.6 Cohort Expansion

The purpose of cohort expansion is to gather additional safety, tolerability, preliminary efficacy and pharmacodynamic information regarding the combination of urelumab and nivolumab. Once the safety profile of all doses tested has been characterized and the MTD of combined administration of urelumab and nivolumab has been defined, cohort expansions will be initiated at the MTD, the HAD, or an alternate dose, if recommended by the investigators and the sponsor. Treatment doses in the cohort expansion groups will not exceed the HAD. The cohort expansion phase will follow a 2-stage design as outlined below in Table 3.1.6-1.

Table 3.1.6-1: Cohort Expansion

Tumor Types	Stage 1 Expansion	Stage 2 Expansion
Non-small Cell Lung Cancer (NSCLC)	Up to approximately 20 subjects at MTD or HAD	Up to approximately 20 additional subjects
Melanoma (MEL)	Up to approximately 20 subjects at MTD or HAD	Up to approximately 20 additional subjects
Head and Neck Squamous Cell Carcinoma (SCCHN)	Up to approximately 20 subjects at MTD or HAD	Up to approximately 20 additional subjects
Diffuse Large B Cell Lymphoma (DLBCL)	Up to approximately 20 subjects at MTD or HAD	Up to approximately 20 additional subjects
NSCLC (progressive or recurrent disease during or after anti-PD-1/anti-PD-L1 therapy)	Up to approximately 20 subjects at MTD or HAD	Up to approximately 20 subjects

Table 3.1.6-1: Cohort Expansion		
Tumor Types	Stage 1 Expansion	Stage 2 Expansion
Follicular Lymphoma (FL)	Up to approximately 20 subjects at MTD or HAD	Up to approximately 20 subjects
Melanoma (progressive or recurrent disease during or after an anti-PD-1/anti-PD-L1 containing treatment regimen)	Up to approximately 20 subjects at MTD or HAD	Up to approximately 20 subjects
Melanoma PD-L1 negative	Up to approximately 50 subjects at MTD or HAD	

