 2. An increase \geq 50% in the size of previously involved sites $>$ 6 months after completing planned therapy.
- iii. Definition of Refractory FL
 1. $<$ 50% decrease in lesion size after planned therapy
 2. The appearance of new lesions during therapy or $<$ 6 months after completion of planned therapy
 3. An increase of \geq 50% in the size of previously involved sites during therapy or $<$ 6 months after completion of planned therapy

g. Melanoma (MEL) Subjects with progressive or recurrent disease (per RECIST v1.1) during or after anti-PD-1 or anti-PD-L1 therapy:

- i. Subjects must have known BRAF V600 mutation status or consent to BRAF V600 mutation testing per local institutional standards during the Screening Period.
- ii. Histologically confirmed unresectable Stage 3 or Stage 4 melanoma as per American Joint Committee on Cancer (AJCC) staging system
- iii. Must have received anti-PD-1/anti-PD-L1 with or without anti-CTLA4 treatment as most recent therapy and have progressed during or after therapy.
- iv. The last dose of prior anti-PD-1/anti-PD-L1 treatment \geq 28 days from initiation of study therapy.
- v. No more than 25% of MEL subjects (5 during stage 1 and 5 during stage 2 of cohort expansion) will be enrolled with primary refractory disease (ie, a BOR of PD per RECIST v1.1). The remaining subjects in the cohort will be subjects with relapsed disease (ie, SD, PR or CR but progressing on therapy).

h. Melanoma (MEL) Subjects with PD-L1 negative

- i. Fresh, pre-treatment biopsies are required.
- ii. Subjects must have known BRAF V600 mutation status or consent to BRAF V600 mutation testing per local institutional standards during the Screening Period.
- iii. Histologically confirmed unresectable Stage 3 or Stage 4 melanoma as per American Joint Committee on Cancer (AJCC) staging system
- iv. Treatment naive subjects (ie, no prior systemic anticancer therapy for unresectable or metastatic melanoma).
 1. Note: Prior adjuvant or neoadjuvant melanoma therapy is permitted if it was completed at least 4 weeks or 5 half-life times (whichever is shorter) prior to randomization and all related adverse events have either returned to baseline or stabilized. However, no prior therapy with immune checkpoint inhibitors (eg, anti-PD-1, anti-PD-L1, anti LAG 3 and anti-CTLA4); immune costimulatory molecules (eg, anti-CD137, anti-OX40, anti GITR); anti-cancer vaccines (eg, Provenge, MAGE-3); or other immune modulating monoclonal antibodies is permitted.

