## **2.4 Protocol Amendments**

This statistical analysis plan (SAP) incorporates the global protocol amendments listed in Table 6.

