**Table 6: Protocol Amendments**

Amendments	Date of Issue	Summary of Major Changes
Amendment 01	09-Jul-2014	Inclusion of pharmacogenetic data collection and statistical analysis
Amendment 02	06-Mar-2015	Updates to the inclusion/exclusion criteria, re-treatment phase, and PK sampling and biomarker assessments.
Amendment 03	29-Jun-2015	Changed Nivolumab dosing from mg/kg to mg flat dosing, updated the duration of therapy for both drugs, updates made to the PK endpoints and analyses.
Amendment 04	30-Aug-2015	Removed randomization and Q8W dosing arms from cohort expansion.
Amendment 05	22-Dec-2015	Added 2 tumor types (NSCLC-PROG and FL).

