## **7 STATISTICAL ANALYSES**

### **7.1 General Methods**

All analyses will be performed in SAS using version 9.2 or higher. Some figures may be generated using S-Plus.

Continuous variables will be summarized by treatment group using the mean, standard deviation, median, minimum, and maximum values. Some continuous variables may also be summarized

using the geometric mean and coefficient of variation. Categorical variables will be summarized by frequencies and percentages. Percentages will be rounded and may not always add up to 100. Percentages less than 0.1 will be indicated as “< 0.1”.

In general, all analyses will be presented by tumor type and treatment group, unless otherwise specified. There will be 9 categories: NSCLC-NAIVE, MEL, SCCHN, DLBCL, NSCLC-PROG, FL, Other Solid, Other Blood, and All Comers, where sufficient data is available, unless otherwise specified.

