**Summary:**

The following subject demographics and baseline characteristics will be summarized by treatment arm and overall using descriptive statistics or frequency statistics.

- Age (in years); age category (<65, ≥65)
- Gender
- Race
- Ethnicity (for US only)
- Height
- Baseline Weight
- Baseline ECOG status
- Disease characteristics
  - For NSCLC (both NSCLC-NAIVE and NSCLC-PROG): stage at initial diagnosis and at study entry, cell type, EGFR mutation status, ALK translocation status, tobacco use status, electronic cigarette use status, PD-L1 level
  - For MEL: stage and M status at initial diagnosis and at study entry, subtype of disease, BRAF mutation status, PD-L1 level
  - For SCCHN: stage at initial diagnosis and at study entry, cell type, location, viral tumor status
  - For DLBCL and FL: stage at initial diagnosis and at study entry, IPI score
  - For tumor types that are not NSCLC-NAIVE, MEL, SCCHN, DLBCL, NSCLC-PROG, and FL, the diagnosis will be presented in a frequency table, along with their stage at study entry

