**7.5.1      *Other Observations Related to Efficacy***

**Summary:**

- Certain efficacy analyses in [Section 7.5](#) are expected to be repeated by mutation status (eg, EGFR, BRAF), HPV status, IPI score, or other clinically meaningful disease characteristic, if there are sufficient data. These will be detailed in the DPP.

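### The visible SAP stops at Amendment 05: post-anti-PD-1 melanoma has no reporting category of its own, and the protocol's 68-patient PD-L1-negative response rate is missing from the SAP's sample-size and efficacy sections

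*SAP*

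**What the plan says.** SAP 2.4 defines its own scope: "This statistical analysis plan (SAP) incorporates the global protocol amendments listed in Table 6". The last row of Table 6 is Amendment 05 (22-Dec-2015), recorded as "Added 2 tumor types (NSCLC-PROG and FL". SAP Table 5 accordingly has one melanoma row. SAP 7.1 lists the presentation groups: "There will be 9 categories: NSCLC-NAIVE, MEL, SCCHN, DLBCL, NSCLC-PROG, FL, Other Solid, Other Blood, and All Comers". SAP 7.3.2 gives a single set of baseline items: "For MEL: stage and M status at initial diagnosis and at study entry, subtype of disease, BRAF mutation status, PD-L1 level".

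The protocol went further. Its document history gives the purpose of Amendment 06 (09-May-2016) as "To include a cohort of NSCLC and melanoma subjects who have relapsed or are refractory to prior anti-PD-1/anti-PD-L1 therapy". Amendment 08 (22-Mar-2017) added untreated PD-L1-negative melanoma. The current Table 3.1.6-1 in protocol 3.1.6 has three melanoma rows, one of them "Melanoma (progressive or recurrent disease during or after an anti-PD-1/anti-PD-L1 containing treatment regimen". For that cohort, protocol 3.3.1 (cohort g) says: "Must have received anti-PD-1/anti-PD-L1 with or without anti-CTLA4 treatment as most recent therapy and have progressed during or after therapy".

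Protocol 8.1.2.2 plans to combine 50 new untreated PD-L1-negative melanoma patients with about 18 from Cohort 2. It states that 38 responders of 68 would put the 95% Clopper-Pearson lower limit above 42%.

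**The concern.** Efficacy and safety are to be reported by tumor type, so a cohort without a category has no planned estimate. The SAP separates NSCLC-NAIVE from NSCLC-PROG because prior anti-PD-1/PD-L1 exposure defines a different population. It makes no such split for melanoma, where the protocol now draws the same line. The pattern looks like a SAP that was not updated, rather than a decision to pool.

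Two things are at stake. The first is the melanoma result. Mixing pretreated with untreated patients would give a rate that describes neither group and that moves with the enrolment mix. The second is the 68-patient PD-L1-negative ORR. It is the estimate for which the protocol sizes the 50-patient addition, yet the SAP sections where one would look for its population and pooling rule do not mention it.

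**Working it through.** **1. Text comparison.**

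| Current protocol cohort | Place in the SAP as written |
|---|---|
| b: untreated melanoma | MEL |
| h: untreated PD-L1-negative melanoma | Fits MEL, not distinguished |
| g: post-anti-PD-1/PD-L1 melanoma | No fitting category: MEL or Other Solid |

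**2. Conflict with the entry check.** SAP 7.2.3 lists prior systemic therapy for metastatic melanoma as a relevant deviation in the MEL cohort. Cohort g requires anti-PD-1/PD-L1 as the most recent therapy. If cohort g is filed under MEL, the check would generally flag patients for meeting their own entry criterion. I say generally because prior therapy given only as adjuvant treatment might not trigger it.

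**3. Size of the cohort without a category.** Protocol Table 3.1.6-1 has seven cohorts of 20 in Stage 1 (plus 20 more each if Stage 2 opens) and one cohort of 50.
- No Stage 2 opened: 7 × 20 + 50 = 190; cohort g is 20/190 = 10.5%.
- All Stage 2 opened: 7 × 40 + 50 = 330; cohort g is 40/330 = 12.1%.

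**4. Effect of pooling (illustration).** Inputs:
- 23/46 responders in earlier melanoma patients (protocol 1.5), all assumed untreated;
- 28/50 in the new PD-L1-negative cohort, which is the protocol's assumed 56%;
- n = 20 or 40 post-anti-PD-1 patients with an assumed ORR r of 5% to 20%.

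Pooled ORR = (23 + 28 + r·n) / (46 + 50 + n).

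| r | n = 20 | n = 40 |
|---|---|---|
| 5% | 52/116 = 44.8% | 53/136 = 39.0% |
| 10% | 53/116 = 45.7% | 55/136 = 40.4% |
| 20% | 55/116 = 47.4% | 59/136 = 43.4% |

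Untreated only: 51/96 = 53.1%.

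**5. The protocol's figure for 68 patients.** The Clopper-Pearson lower limit is the 0.025 quantile of Beta(x, n − x + 1), and the upper limit is the 0.975 quantile of Beta(x + 1, n − x).
- 38/68 = 55.9%, 95% CI 43.3% to 67.9%. The protocol's statement reproduces.
- 37/68: lower limit 41.9%. So 38 is the smallest count that clears 42%.

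**6. Where the SAP could hold this analysis.** SAP 5.2.1 and 5.2.2 cover n = 20 and n = 40 only. SAP 7.5 plans the same interval method for ORR but names no PD-L1-negative population and no rule for combining 50 with about 18. SAP 7.8.1, on PD-L1 expression, cannot be read in the public copy.

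**7. Who the 18 are.** Protocol 8.4.2 adds escalation patients to expansion patients by disease type and treatment, not by prior therapy. Escalation entry generally required a prior regimen, with exceptions, whereas the 50 new patients must be untreated. The documents do not say how many of the 18, if any, came from escalation.

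**The case against.** The strongest reply is that the SAP is more flexible than its list suggests. The 7.1 categories are introduced as a general rule and are followed by a qualifier that allows exceptions. SAP 7.5.1 expects some efficacy analyses to be repeated by mutation status, "HPV status, IPI score, or other clinically meaningful disease characteristic, if there are sufficient data", with details left to the data presentation plan. So the nine categories are not immovable. Even so, neither provision names prior anti-PD-1 exposure or PD-L1 status, and neither commits to a separate estimate.

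Several stronger readings are tempting, and the documents do not support them:
- **That both later melanoma cohorts are stranded.** The PD-L1-negative cohort is untreated melanoma and fits MEL. Only the post-anti-PD-1 cohort lacks a fitting category.
- **That the ORR denominator is undefined.** SAP 7.5 already plans efficacy on both All Treated and Response Evaluable subjects. The requirement of at least two on-treatment scans is written in the protocol as an accrual rule, not as an analysis set.
- **That 42% is a threshold which could be missed.** It illustrates precision. The study tests no formal hypothesis, and nothing is decided at that value.
- **That the Stage 2 decision is affected.** Protocol 3.1.6.1 applies it per tumor-specific cohort through sponsor and investigator review. SAP reporting groups do not change that.
- **That no PD-L1-by-response analysis exists.** SAP 7.8.1 may contain one. The statement here is confined to the visible sample-size and efficacy sections.

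SAP 7.2.3 also provides for an amendment if an unlisted relevant deviation is found before final lock. That helps with missing checks. It does not correct an existing check that flags the wrong patients.

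**Conclusion.** The point holds in a limited form: the visible SAP lags the current protocol by the two amendments that added melanoma cohorts. The firm consequence is for the post-anti-PD-1 melanoma cohort of 20 to 40 patients, about 10.5% to 12.1% of expansion at full cohort sizes. As written, it has no ORR, DOR, PFS, OS or safety estimate of its own, and under MEL its patients would generally be listed as deviations. The gap of 39% to 47% against 53% is an illustration. It rests on the assumed response rates and on treating all 46 earlier melanoma patients as untreated, which the protocol does not state.

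The 68-patient analysis is correctly calculated in the protocol but not carried into the visible SAP sample-size or efficacy text. Safety summarized over all patients is unaffected. This should be corrected before the final analysis, but it does not undermine the trial's primary safety objective.

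**What to change.** Amend the SAP for Amendments 06 and 08:
- **Table 5, 7.1 and 7.3.2:** add MEL-PROG, separate from untreated MEL and mirroring NSCLC-PROG.
- **7.2.3:** limit the prior-systemic-therapy check to the untreated melanoma cohorts, and add a check for MEL-PROG that prior anti-PD-1/PD-L1 therapy was received.
- **5.2.2 and 7.5:** add the pooled PD-L1-negative untreated melanoma ORR with its 95% Clopper-Pearson interval, on All Treated with Response Evaluable as the second set, as 7.5 already plans. Restrict the Cohort 2 contribution to patients who meet the same untreated criterion, or show any pretreated patients separately.

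The cost is one SAP amendment and no new data. The melanoma cells become smaller and their intervals wide (4/20, for example, has a 95% interval of 5.7% to 43.7%), and about 18 patients will appear in two outputs, which should be footnoted.

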## **7.2 Study Conduct**

### **7.2.1 Study Information**

#### **Listing:**

- Batch number will be listed by batch number and subject. It is noted that a subject may appear multiple times under different batch numbers.

### **7.2.2 Accrual**

The following will be presented on the All Enrolled Subjects.

#### **Summary:**

- Number (%) of subjects enrolled and treated, by country and investigational site

#### **Listing:**

- Subjects accrued by country and investigational site

### **7.2.3 Relevant Protocol Deviations**

A relevant protocol deviation is a deviation from the protocol which is programmed in the database and which could potentially affect the interpretability of the study results. Non-programmable relevant eligibility and on-treatment protocol deviations, as well as significant (both programmable and non-programmable) will be reported through ClinSIGHT listings. The following programmable deviations from inclusion and exclusion criteria will be considered as relevant protocol deviations and a listing will be provided. During the conduct of the trial, if any relevant protocol deviation is discovered that is not on this list, this SAP should be amended prior to the final database lock. Relevant protocol deviations, their implications, and subsequent actions will be reported in the CSR.

#### **At Entrance:**

- For Cohort Expansion only:
  - For the NSCLC-NAIVE cohort
    - ◆ Subjects with prior anti-PD-1/anti-PD-L1 therapy (Inclusion Criteria 2.a.ii.1.a)
    - ◆ Subjects with unknown EGFR or ALK status (Inclusion Criteria 2.a.ii.1.a)
  - For the MEL cohort
    - ◆ Subjects with prior systemic therapy for metastatic melanoma (Inclusion Criteria 2.a.ii.1.b.iv)

- ◆ Subjects with unknown BRAF V600 status (Inclusion Criteria 2.a.ii.1.b.ii)
- ◆ Subjects without histologically confirmed unresectable Stage III or Stage IV melanoma, as per American Joint Committee on Cancer (AJCC) staging system (Inclusion Criteria 2.a.ii.1.b.iii)
- For the SCCHN cohort
  - ◆ Subjects without histologically confirmed incurable locally advanced, recurrent or metastatic SCCHN, Stage III/IV (Inclusion Criteria 2.a.ii.1.c.i)
- For the DLBCL cohort
  - ◆ Subjects without at least one lesion that is > 15 mm (1.5 cm) in the longest diameter (Inclusion Criteria 2.a.ii.1.d.v)
- For the NSCLC-PROG cohort
  - ◆ Subjects with non-squamous histology and unknown EGFR or ALK status (Inclusion Criteria 2.a.ii.1.e.iii)
  - ◆ Subjects without prior anti-PD-1/anti-PD-L1 therapy (Inclusion Criteria 2.a.ii.1.e.vi)
  - ◆ Subjects with prior anti-PD-1/anti-PD-L1 therapy with a dose date within 28 days of first dose of study therapy (Inclusion Criteria 2.a.ii.1.e.vii)
- For the FL cohort
  - ◆ Subjects without prior rituximab therapy (Inclusion Criteria 2.a.ii.1.f.i)
- Subjects without measurable disease at baseline (Inclusion Criteria 2.b)
- Subjects with baseline ECOG performance status > 1, at the screening visit only (Inclusion Criteria 2.f)
- Subjects who have previously received nivolumab, anti-CTLA4 within 100 days, or any other anti-cancer therapy within 4 weeks prior to first dose (Exclusion Criterion 1d, 3b, and 3c)

### **On-Treatment:**

- Subjects receiving anti-cancer therapy (chemotherapy, hormonal therapy, immunotherapy, standard or investigational agents for treatment of cancer) before the last dose of study therapy
  - In the event that this occurs, this will be treated as subject's subsequent therapy for certain efficacy assessments described in [Section 4.2.1](#) (eg, BOR and DOR).
- Subjects receiving doses or frequencies that is different than what they were assigned
  - In the event that this occurs, subjects may be grouped with the actual treatment received, rather than the assigned treatment, for the analyses.
- During the first dosing visit, if subjects receive urelumab dose first, before receiving the nivolumab dose

## **7.3 Study Population**

### **7.3.1 Subject Disposition**

#### **Summary:**

- Screening phase: The number (%) of subjects of the following will be summarized on the population of All Enrolled Subjects.
  - All enrolled into the study
  - Entering the treatment phase
  - Enrolled but not entering the treatment phase together with the reasons
- End of treatment phase: The number (%) of subjects of the following will be summarized by treatment group and overall, based on the population of All Treated Subjects.
  - All treated subjects
  - Subjects continuing in the treatment phase
  - Subjects not continuing in the treatment phase together with the reasons
  - Subjects continuing in the study
- End of follow-up phase: The number (%) of subjects of the following will be summarized by treatment group and overall, based on the population of All Treated Subjects.
  - All treated subjects
  - Subjects continuing in the next phase
  - Subjects not continuing in the next follow-up phase together with the reasons
- End of survival follow-up phase: The number (%) of subjects of the following will be summarized by treatment group and overall, based on the population of All Treated Subjects.
  - All treated subjects
  - Subjects continuing in the survival follow-up phase
  - Subjects not continuing in the survival follow-up phase together with the reasons

**Listing:**

- Screen failures: Subjects who discontinued from the study pre-treatment for screen failures will be listed with the reason for screen failure
- Subject status at:
  - End of treatment phase
  - End of follow-up phase
  - End of survival follow-up phase
- Re-treatment subject status at:
  - End of re-treatment phase
  - End of follow-up phase for re-treatment eligible subjects

